8.1.2 Exclusion criteria

- ◆ CML in accelerated phase or blastic crisis as defined by the WHO criteria (see appendix A).
- ◆ Hepatic dysfunction (serum bilirubin $\geq 2 \times N$, and/or ALAT $\geq 4 \times N$, and/or ASAT $\geq 4 \times N$);
- ◆ Renal dysfunction (creatinine $\geq 200 \mu\text{mol/l}$ or 2.3 mg/dl);
- ◆ Severe cardiac dysfunction (NYHA classification II-IV, see appendix F);
- ◆ Severe pulmonary or neurologic disease;
- ◆ Pregnant or lactating females;
- ◆ Patients with a history of active malignancy during the past 5 years with the exception of basal carcinoma of the skin or stage 0 cervical carcinoma;
- ◆ Patients known to be HIV-positive;
- ◆ Patients with active, uncontrolled infections;
- ◆ Previous treatment other than hydroxyurea ≤ 2 months or imatinib ≤ 1 month;
- ◆ Male and female patients of reproductive potential who are not practicing effective means of contraception.

9 Treatments

9.1 Imatinib monotherapy (arm A)

Following registration and randomization, preceding therapy with hydroxyurea or imatinib is stopped and imatinib is started at a total dose of 800 mg daily, preferably 2 x 400 mg 12 hours apart.

Imatinib is continued until progression or intolerance of treatment (see section 10).

9.1.1 Dose adjustments during imatinib monotherapy

Hematological toxicity

Grade 1 and 2:

No dose adjustments for grade 1 and 2 hematological toxicity will be made.

Grade 3 and 4:

If a patient experiences a grade ≥ 3 neutropenia and/or thrombocytopenia (i.e., ANC $< 1.0 \times 10^9/l$, or a platelet count $< 50 \times 10^9/l$), imatinib must be withheld until the toxicity has resolved to grade ≤ 2 .

ANC takes precedence over WBC in determining the degree of neutropenia. If the hematological toxicity resolves to grade ≤ 2 within 2 weeks, imatinib may be resumed at a dose of 800 mg/day, as appropriate. If the grade ≥ 3 hematological toxicity recurs or persists for longer than two weeks, imatinib must be withheld and reduced to 600 mg/day once toxicity has resolved to grade ≤ 2 . If the grade ≥ 3 hematological toxicity recurs after dose reduction to 600 mg, imatinib must be withheld and may be resumed at 600 mg/day upon recovery to grade ≤ 2 . If the grade ≥ 3 hematological toxicity recurs, imatinib must be withheld and reduced to 400 mg/day once toxicity has resolved to grade ≤ 2 .

If the grade ≥ 3 neutropenia and/or thrombocytopenia recurs after dose reduction to 400 mg/day, imatinib must be withheld and resumed at 400 mg/day upon recovery to grade ≤ 2 . If the grade ≥ 3 hematological toxicity recurs, imatinib must be withheld and reduced to 300 mg/day upon recovery to grade ≤ 2 . If the grade ≥ 3 hematological toxicity recurs after dose reduction to 300 mg/day, imatinib must be withheld and resumed at 300 mg/day upon recovery to grade ≤ 2 . If at any time the hematological toxicity does not resolve to grade ≤ 2 in 28 days, consult with the study coordinator.

No dose reductions will be performed for grade ≥ 3 anemia or lymphopenia. Patients developing anemia may be transfused or prescribed erythropoietin at the discretion of the treating physician.

Non-hematological toxicity

Grade 1:

No dose adjustments for grade 1 non-hematological toxicity will be made.

Grade 2:

If a patient experiences a grade 2 non-hematological toxicity that does not resolve despite

therapeutic intervention, imatinib must be withheld until the toxicity has resolved to grade ≤ 1 . Imatinib may then be resumed at a dose of 800 mg. If the grade 2 toxicity recurs, imatinib must again be withheld until the toxicity has resolved to grade ≤ 1 , and the dose of imatinib must be reduced to 600 mg daily. If the grade 2 toxicity recurs at 600 mg, imatinib must be withheld until the toxicity has resolved to grade ≤ 1 , and resumed at 600 mg daily. If the grade 2 toxicity recurs at 600 mg, imatinib must again be withheld until the toxicity has resolved to grade ≤ 1 , and imatinib must be resumed at 400 mg daily. If the grade 2 toxicity recurs at 400 mg, imatinib must be withheld until the toxicity has resolved to grade ≤ 1 , and the dose of imatinib must be reduced to 300 mg daily.

Grade 3 and 4:

If a patient experiences grade ≥ 3 non-hematological toxicity, imatinib must be withheld until the toxicity has resolved to grade ≤ 1 . Imatinib may then be restarted at a reduced dose of 600 mg daily. If the grade ≥ 3 toxicity recurs at 600 mg, imatinib must be withheld until the toxicity has resolved to grade ≤ 1 . Imatinib may then be reintroduced at a dose of 400 mg daily. If the toxicity recurs with grade ≥ 3 at 400 mg, imatinib must be withheld until the toxicity has resolved to grade ≤ 1 . Imatinib may then be reintroduced at a dose of 300 mg daily. If at any time the non-hematological toxicity does not resolve to grade ≤ 1 in 28 days, consult with the study coordinator. A documented grade ≥ 3 non-hematological toxicity that recurs despite dose reduction to 300 mg daily is considered intolerance of treatment and the patient should be discontinued from study treatment.

Dose	Hematological toxicity		Non-hematological toxicity	
	Grade 1 and 2	Grade \geq 3	Grade 2	Grade \geq 3
800 mg/day	No dose reduction	Hold therapy and resume at 800 mg after recovery to grade \leq 2 If toxicity recurs, hold therapy and resume at 600 mg after recovery to grade \leq 2	Hold therapy and resume at 800 mg after recovery to grade \leq 1 If toxicity recurs, hold therapy and resume at 600 mg after recovery to grade \leq 1	Hold therapy and resume at 600 mg after recovery to grade \leq 1
600 mg/day	No dose reduction	Hold therapy and resume at 600 mg after recovery to grade \leq 2 If toxicity recurs, hold therapy and resume at 400 mg after recovery to grade \leq 2	Hold therapy and resume at 600 mg after recovery to grade \leq 1 If toxicity recurs, hold therapy and resume at 400 mg after recovery to grade \leq 1	Hold therapy and resume at 400 mg after recovery to grade \leq 1
400 mg/day	No dose reduction	Hold therapy and resume at 400 mg after recovery to grade \leq 2 If toxicity recurs, hold therapy and resume at 300 mg after recovery to grade \leq 2	Hold therapy and resume at 300 mg after recovery to grade \leq 1	Hold therapy and resume at 300 mg after recovery to grade \leq 1
300 mg/day	No dose reduction	Hold therapy and resume at 300 mg after recovery to grade \leq 2 If toxicity recurs at 300 mg, consult with the study coordinator	If toxicity recurs at 300 mg, consult with the study coordinator	Discontinue therapy

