9.1.2 Dose re-escalation during imatinib monotherapy

Every attempt to increase the dose of imatinib to the previously administered dose level prior to any dose reduction should be made. The dose of imatinib should be increased if the following criteria are met at least one month after dose reduction:

- ♦ there is not recurrence of the toxicity which led to dose reduction;
- ♦ there are no additional grade ≥ 2 non-hematological toxicities.

This applies to either dose reductions due to hematological or non-hematological toxicities.

For patients whose imatinib has been reduced to 300 mg, the imatinib dose would be increased to 400 mg. After at least one month the same criteria should once again be met for further dose re-escalations.

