9.1.3 Special management orders in conjunction with imatinib monotherapy

- ♦ Myelosuppression can occur at any time during imatinib therapy, but it generally occurs within 2 to 4 weeks. Use of growth factors (G-CSF and GM-CSF) may be initiated with recurrent grade ≥ 3 neutropenia. Dose titration is recommended to keep ANC $> 1.5 \times 10^9/l$. Dose adjustments should be made according to section 9.1.1.
- ♦ In most cases rash is mild, self-limiting and manageable with antihistamines or topical steroids. A short course of oral steroids may be initiated for the management of more severe cases. Prednisone 25 mg is recommended for one week or until rash has resolved.
- ♦ Patients should be monitored closely for peripheral edema and rapid weight gain. The use of diuretics may be initiated for the management of edema. In severe cases imatinib should be withheld and the edema may be controlled with diuretics. Imatinib can be resumed, while maintaining or increasing diuretic therapy.
- ♦ Routine liver function tests should be performed throughout the study. It is also recommended that patients be screened for viral hepatitis at the screening visit. Dose reduction may be warranted and the decision to continue imatinib needs to be made in light of the clinical situation.

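### Section 9.1.1 gives two restart doses after a first grade 3 or higher neutropenia or thrombocytopenia lasting over two weeks at 800 mg: 600 mg in the text, 800 mg in the table

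*Protocol*

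**What the plan says.** Section 9.1.1 of the protocol sets the imatinib dose rules for monotherapy, first in text and then in a table by dose level.

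For grade 3 or higher neutropenia or thrombocytopenia at 800 mg/day, the text makes the restart dose depend on how long the episode lasts. If it resolves to grade 2 or lower "within 2 weeks, imatinib may be resumed at a dose of 800 mg/day, as appropriate". If it "recurs or persists for longer than two weeks, imatinib must be withheld and reduced to 600 mg/day once toxicity has resolved" to that grade. A further sentence covers toxicity that has not resolved "in 28 days, consult with the study coordinator".

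The table's 800 mg/day row, hematological grade 3 or higher column, reads: "Hold therapy and resume at 800 mg after recovery to grade" 2 or lower, followed by "If toxicity recurs, hold therapy and resume at 600 mg after recovery to grade" 2 or lower. It does not mention duration.

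The section does not say whether the text or the table takes precedence.

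**The concern.** For one clinical event the two instructions give different doses. When a first grade 3 or higher cytopenia at 800 mg takes more than two weeks to recover, the text requires a reduction to 600 mg, while the table sends the patient back to the full dose.

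The event is foreseeable. Section 9.1.3 says of myelosuppression on imatinib that "it generally occurs within 2 to 4 weeks", and section 5.1 reports that it was more frequent at high dose. A site working from the table would restart at 800 mg after a prolonged cytopenia, where the text calls for a lower dose. A monitor would have no stated basis for deciding whether that restart is a deviation. Delivered imatinib dose-intensity is also a secondary endpoint (section 14), so avoidable variation between sites would enter it.

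**Working it through.** No sample size, power or error-rate figure is involved. The check compares the two sets of rules and then sizes the dose difference.

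**Rules side by side, at 800 mg/day, neutropenia or thrombocytopenia of grade 3 or higher**

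| Situation | Text | Table | Agree? |
|---|---|---|---|
| First episode, recovered within 2 weeks | 800 mg | 800 mg | yes |
| First episode, lasting more than 2 weeks | 600 mg | 800 mg | **no** |
| Recurrence after restart at 800 mg | 600 mg | 600 mg | yes |

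**Does another rule settle it?**

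- The 28-day rule applies only to toxicity still unresolved at 28 days. First episodes that resolve on days 15 to 28 remain in conflict.
- The discretion in the text attaches to the branch that recovers within two weeks. The longer branch is mandatory.
- At 600, 400 and 300 mg the text has no two-week condition, and the restart doses match the table. The conflict is confined to one cell.
- Section 9.2.1 has its own rules for arm B from the start of cytarabine until hematological recovery after the last combination cycle. It does not bear on monotherapy, where 9.1.1 governs both arms.

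**Size of the difference for one affected patient**

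- Daily gap: 800 − 600 = 200 mg; 200 / 800 = 25%.
- Planned 12-month dose: 800 × 365 = 292,000 mg.

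*Re-escalation at the earliest point.* Section 9.1.2 says: "The dose of imatinib should be increased if the following criteria are met at least one month after dose reduction". Taking one month as 30 days:

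- 200 × 30 = 6,000 mg; 6,000 / 292,000 = 2.1%.

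*Upper bound.* Assume no re-escalation by month 12 under the text, no recurrence under the table, onset at 2 to 4 weeks (section 9.1.3) and a hold of 15 to 28 days:

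- Earliest restart: day 14 + 15 = 29, leaving 365 − 29 = 336 days. 200 × 336 = 67,200 mg; 67,200 / 292,000 = 23.0%.
- Latest restart: day 28 + 28 = 56, leaving 365 − 56 = 309 days. 200 × 309 = 61,800 mg; 61,800 / 292,000 = 21.2%.

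The protocol does not give the frequency of first episodes lasting more than two weeks, so these per-patient figures cannot be turned into a trial-level effect.

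**The case against.** The best defence is that the table is shorthand for the text beside it. It omits other qualifiers too: the 28-day consultation in this row, the anemia and lymphopenia exception, and the condition that grade 2 non-hematological toxicity must have failed to resolve under treatment. The text addresses this exact case in mandatory terms, whereas the table is merely silent on duration. Someone who reads the whole section would probably follow the text. That lowers the weight of the point but does not remove it. The table is not labelled a summary, it carries operative instructions, and this cell followed literally gives a different dose.

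Two further objections limit the size, and both stand.

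- **Arm B.** Cytarabine starts preferably within 14 days, and at the latest 4 weeks, after imatinib (section 9.2), and section 9.2.1 then applies. In the early window used for the upper bound, the conflict is therefore largely an arm A matter. It reaches arm B mainly in later monotherapy, when less of the 12 months remains.
- **The upper bound is unlikely.** Section 9.1.2 wants every effort made to re-escalate, and a recurrence at 800 mg leads to 600 mg under the table as well, so the two readings converge. A patient who cannot re-escalate because of toxicity is a poor candidate for a full year at 800 mg. The 2.1% figure, which follows the re-escalation rule at its earliest point, is the more relevant one.

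**Conclusion.** The inconsistency is real, narrow and minor. It concerns a first grade 3 or higher neutropenia or thrombocytopenia at 800 mg that lasts more than two weeks, in practice mainly one resolving between day 15 and day 28. The two readings differ by 200 mg/day from restart. For an affected patient that is 2.1% of the planned 12-month dose with re-escalation after 30 days; the 21.2% to 23.0% range is an upper bound under the assumptions stated.

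Both readings withhold imatinib until grade 2 or lower, so the issue is the restart dose alone. It matters for safety and for consistent dosing across sites. No effect on the 12-month major molecular response comparison and no bias between arms is claimed.

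**What to change.** Reword the hematological grade 3 or higher cell of the 800 mg/day row so that it carries the text's own condition, for example:

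> Interrupt imatinib. Restart at 800 mg if the toxicity has come down to grade ≤ 2 within 2 weeks. If it lasts longer than 2 weeks, or returns, restart at 600 mg once it is grade ≤ 2.

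As an optional tidy-up, label the column *Neutropenia/thrombocytopenia*, to match the text's exclusion of anemia and lymphopenia from dose reduction.

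The cost is one table cell and, if wanted, one column label. A clarification letter or the next amendment would do. The fix introduces no new rule.

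### Protocol 9.1.1: the dose table orders an imatinib hold for any grade 2 non-hematological toxicity, while the text does so only when treatment has failed to resolve it

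*Protocol*

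**What the plan says.** The Grade 2 paragraph under non-hematological toxicity in Protocol 9.1.1 opens with a conditional rule: "If a patient experiences a grade 2 non-hematological toxicity that does not resolve despite" and, in the same sentence, "therapeutic intervention, imatinib must be withheld until the toxicity has resolved to grade" 1 or lower. The patient may then restart at 800 mg.

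The sentences on recurrence carry no such condition. The first reads "If the grade 2 toxicity recurs, imatinib must again be withheld until the toxicity has resolved to grade" 1 or lower, with a reduction to 600 mg. Further recurrences lead to a hold and restart at 600 mg, then 400 mg. The last step is "If the grade 2 toxicity recurs at 400 mg, imatinib must be withheld until the toxicity has resolved to grade" 1 or lower, followed by 300 mg.

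The dose table closes the section. Its Grade 2 non-hematological column reads:

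- 800 mg row: "Hold therapy and resume at 800 mg after recovery to grade" 1 or lower; on recurrence, hold and restart at 600 mg.
- 600 mg row: "Hold therapy and resume at 600 mg after recovery to grade" 1 or lower; on recurrence, hold and restart at 400 mg.
- 400 mg row: hold and restart at 300 mg, with no distinction between a new event and a recurrence.
- 300 mg row: "If toxicity recurs at 300 mg, consult with the study coordinator".

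None of these cells mentions a prior attempt at treatment. The table is not labelled a summary, and the protocol does not say whether text or table takes precedence. Arm A follows 9.1.1 throughout; arm B follows it once the cytarabine phase is over (9.2.1 and 9.3).

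**The concern.** Both versions are mandatory instructions in one section, and they give different answers for the same patient. Suppose a new grade 2 rash settles with topical treatment. Under the text the patient continues without interruption; under the table the patient stops. If that patient is already at 400 mg because of another toxicity, the table also lowers the dose to 300 mg, where the text asks for no change. Two sites can therefore act differently and each be following 9.1.1.

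Dose rules of this kind belong in the protocol, so this is not a detail awaiting a statistical analysis plan. An unintended hold also works against the protocol's own aims: 9.1.2 asks for every attempt to restore the dose, and delivered imatinib dose-intensity is a secondary endpoint (section 14).

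**Working it through.** **Step 1: text against table, by situation (grade 2 non-hematological, imatinib monotherapy).**

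| Situation | Text | Table |
|---|---|---|
| No earlier hold for this toxicity, treatment controls it, at 800 mg | no hold | hold, restart at 800 mg |
| Same, at 600 mg | no hold | hold, restart at 600 mg |
| Same, at 400 mg | no hold | hold, restart at 300 mg |
| Recurrence after an earlier hold, at 800, 600 or 400 mg | hold, same dose steps as table | hold, same dose steps as text |
| Grade 2 recurrence at 300 mg | silent | consult the study coordinator |

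The 600 and 400 mg entries under the text follow because its opening condition names no dose level, while its sentences for 600 and 400 mg concern only a toxicity that recurs. On the trigger, the disagreement is confined to the first three rows.

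**Step 2: which rule was probably meant.** Section 9.4 places loperamide for diarrhea of grade 2 or worse ahead of interrupting imatinib. Section 9.1.3 treats rash first and reserves withholding for severe edema. These fit the text. They are limited evidence: each covers one toxicity, the loperamide provision is permissive, and the rash and edema orders state no grade. The table also omits two other qualifiers found in the text, the two-week rule for cytopenia and the exception for anemia and lymphopenia. That fits a condensed version of the text. The intent is therefore inferred, not stated.

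**Step 3: cost per affected patient, table instead of text, as a share of one year at the current dose.**

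- One day of hold, at any dose level: 1 / 365 = 0.27%.
- Reduction at 400 mg: 9.1.2 allows re-escalation no sooner than one month after a reduction, and only if there is no further non-hematological toxicity of grade 2 or higher. Taking the minimum as 30 days: (400 − 300) × 30 = 3,000 mg; a year at 400 mg is 400 × 365 = 146,000 mg; 3,000 / 146,000 = 2.05%. The hold comes on top.

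The protocol gives no hold duration. Assume 3 to 7 days. Longer holds are left out because the event might then count as one that treatment failed to resolve, where the text also holds.

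- At 800 or 600 mg: 3 / 365 = 0.82% to 7 / 365 = 1.92%.
- At 400 mg: 0.82% + 2.05%, about 2.9%, to 1.92% + 2.05%, about 4.0%.
- Recurrence after an earlier hold: no difference.

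The protocol does not indicate how many patients or sites would be affected, so no trial-level figure can be derived.

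**The case against.** The best defence is that the table directly follows the full text, drops qualifiers elsewhere and would be read as a quick reference to it. The toxicity-specific orders support the same reading, and a careful site would follow the text. The consequence is also small: at 800 or 600 mg it is only an assumed hold of a few days divided by 365. The larger figure needs a patient already at 400 mg who develops a different grade 2 toxicity, has it controlled, and is dosed from the table alone.

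Most of this stands and is why the point is minor. It does not remove the contradiction. Sites cannot treat the table as redundant, because the instruction for a grade 2 recurrence at 300 mg appears only there. Nothing tells them to set it aside at 800, 600 and 400 mg.

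A reader might infer that one sentence giving the text precedence would settle the matter. It would not be safe. The text gives the restart dose after a first hold only as 800 mg. Consider a patient already at 600 or 400 mg with a new grade 2 toxicity that treatment fails to control. Text and table both hold, but a general precedence rule would then select 800 mg over the table's 600 or 300 mg. The same would happen on the hematological side for a patient at 600 mg with a first grade 3 neutropenia that resolves within two weeks. The table's row-specific doses now guard against this.

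**Conclusion.** Wrong as written, minor severity: 9.1.1 contains an internally contradictory dosing rule. It applies to a grade 2 non-hematological toxicity that has not previously required a hold and that treatment controls. The result is an avoidable hold, costing 0.27% of a year's dose per day. At 400 mg there is also a reduction of at least one month, about 2% of a year's dose. The ranges of 0.8 to 1.9% (800 or 600 mg) and 2.9 to 4.0% (400 mg) rest on the assumed 3 to 7 day hold.

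A reader might infer that the mismatch distorts the 12-month major molecular response rate or favours one arm. The protocol does not support that. Both arms use the same section during monotherapy, the frequency of such events is not given, and the loss per patient is small. What can be said is that sites may handle the same event inconsistently.

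**What to change.** Add the text's condition to the Grade 2 non-hematological cells at 800, 600 and 400 mg, for example: *For a toxicity that has not previously required a hold, hold only if therapeutic intervention fails to resolve it; if it recurs after a hold, hold without this condition.* Keep the table's restart dose in each row and leave the 300 mg row as it is. Do not add a general statement that the text prevails.

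The dividing line should be an earlier hold, not a first occurrence. The text's recurrence sentence says imatinib is withheld again, which presupposes an earlier hold. A second episode of a toxicity that was controlled the first time without one would otherwise remain unclear.

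The cost is one addition to three table cells, sent to sites as a clarification. Endpoints, analysis and sample size do not change.

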9.1.2 Dose re-escalation during imatinib monotherapy

Every attempt to increase the dose of imatinib to the previously administered dose level prior to any dose reduction should be made. The dose of imatinib should be increased if the following criteria are met at least one month after dose reduction:

- ♦ there is not recurrence of the toxicity which led to dose reduction;
- ♦ there are no additional grade ≥ 2 non-hematological toxicities.

This applies to either dose reductions due to hematological or non-hematological toxicities.

For patients whose imatinib has been reduced to 300 mg, the imatinib dose would be increased to 400 mg. After at least one month the same criteria should once again be met for further dose re-escalations.

